9.4.1. PK/PD Unblinding Plan

If needed, a PK/PD unblinding plan will be developed for the Main Cohort (Cohort A), Cohort C and Cohort D, to safeguard the study blind for members of the study team. These procedures will be in accordance with applicable Pfizer SOPs for releasing randomization codes and breaking the study blind. Under this plan, a limited number of individuals, not on the study team, will be unblinded, with the purpose of composing PK/PD and/or immunogenicity analysis sets and conducting PK/PD analysis that will not be made available to the study team until after database lock.

9.5. Sample Size Determination

The planned total sample size for the study is up to approximately 781 randomized participants.

Main Cohort (Cohort A)

A sufficient number of participants will be screened to achieve a total of approximately 416 randomized participants, with 380 participants randomly assigned to ponsegromab 300 mg Q4W and placebo Q4W in approximately a 1:1 ratio, plus an additional 36 participants randomly assigned to ponsegromab 100 mg Q4W and 200 mg Q4W in approximately a 1:1 ratio. Participants will be randomized initially in a 1:1:1:1 ratio to all four treatment arms (until approximately 72 participants are randomized), followed by a 1:1 ratio to the 300 mg Q4W and placebo arms only. This planned number of randomized participants is expected to ensure completion of the Main Cohort (Cohort A) of approximately 161 evaluable participants in the 300 mg Q4W and placebo Q4W treatment arms and approximately 15 evaluable participants in the 100 mg and 200 mg Q4W treatment arms, assuming a discontinuation rate of 15% (if this rate is higher, or there is a high rate of non-compliance, more participants may be randomized to ensure the required number of evaluable participants).

The sample size in the ponsegromab 300 mg Q4W and placebo arms is based

CCI

CCI

The sample size in the ponsegromab 100 mg and 200 mg Q4W arms has been chosen empirically to provide sufficient data to gain a preliminary understanding of the PK/PD relationship in this population, and is not based on the primary endpoint.

Open-Label, PK Cohort (Cohort B)

Approximately 20 additional participants will be randomly assigned to open-label ponsegromab 100 mg, 200 mg and 300 mg Q4W in approximately a 1:2:2 ratio. This sample size has been chosen empirically to provide sufficient evaluable participants (approximately 15) to adequately evaluate the PK of ponsegromab following repeated SC administration to participants with HF and elevated circulating GDF-15 concentrations, assuming a 15% discontinuation rate (if this rate is higher, or there is a high rate of non-compliance, more participants may be randomized to ensure the required number of evaluable participants).

Cohort C (optional)

A sufficient number of participants will be screened to achieve a total of approximately 195 randomized participants, with 130 participants randomly assigned to ponsegromab 100 mg Q4W and 65 to placebo Q4W in approximately a 2:1 ratio. This planned number of randomized participants is expected to ensure completion in Cohort C of approximately 110 evaluable participants in the 100 mg Q4W and 55 in the placebo Q4W treatment arms, assuming a discontinuation rate of 15% (if this rate is higher, or there is a high rate of non-compliance, more participants may be randomized to ensure the required number of evaluable participants). This sample size of 165 completers is based on the primary efficacy endpoint and, when combined with the completing 100 mg Q4W and placebo Q4W participants in the Main Cohort (Cohort A), gives similar acceptable Operating Characteristics to those for the 300 mg Q4W arm in the Main Cohort.

CCI

Cohort D (optional)

Approximately 100 participants will be randomly assigned to ponsegromab 300 mg Q4W or placebo in approximately a 1:1 ratio in Cohort D. This sample size has been estimated based on the number of participants being screened for Cohort C and the anticipated screen-fail rate. The actual sample size may be lower or higher than estimated, with a maximum of approximately 150 total participants in this cohort. Enrollment into Cohort D will stop approximately when enrollment into Cohort C stops.

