The sample sizes for the ponsegromab 300 mg and placebo dose groups in the Main Cohort (Cohort A) and for the ponsegromab 100 mg dose group in optional Cohort C were chosen to provide acceptable operating characteristics for the primary endpoint for both doses, and thereby support dose-finding efforts for any subsequent clinical studies. The smaller sample size in the ponsegromab 100 mg and 200 mg Q4W arms in the Main Cohort (Cohort A) was chosen empirically to provide sufficient data to gain a preliminary understanding of the PK/PD relationship in this population. The sample size for the open-label, PK cohort (Cohort B) has been chosen empirically to provide sufficient evaluable participants to adequately evaluate the PK of ponsegromab following repeated SC administration to participants with HF and elevated circulating GDF-15 concentrations. The sample size for the optional Cohort D was chosen empirically to provide data on participants with GDF-15 levels CCI pg/mL for supportive analyses.

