## 5.2. General Methods

*Following PCD, the data will be analyzed and reported in a CSR. The results for the open-label, PK cohort (Cohort B) may be reported in a separate CSR.*

*For safety analyses and PK/PD/immunogenicity analyses, the Main Cohort (Cohort A) and Cohort C will be reported combined, with data from the same treatment group combined across cohorts; the open-label, PK cohort (Cohort B) will be reported separately; Cohort D will be reported separately.*

Efficacy analyses will be produced using 4 different approaches:

1. Main Cohort (Cohort A) only: The main efficacy analyses for the 300 mg ponesegromab treatment group will be performed using data from the Main Cohort (Cohort A) only; statistical models will include data from the 300 mg ponesegromab treatment group and placebo only. Summaries will include data from all treatment groups.
2. The open-label, PK cohort (Cohort B) only: The open-label, PK cohort (Cohort B) will be presented separately from the Main Cohort (Cohort A), Cohort C and Cohort D.
3. Main Cohort (Cohort A) and Cohort C combined: The main statistical analyses for the 100 mg and 200 mg ponesegromab treatment groups will be performed using combined data from the Main Cohort (Cohort A) and Cohort C; statistical models will include data from all three ponesegromab treatment groups and placebo, with these analyses also providing sensitivity analyses for the 300 mg ponesegromab treatment group. Summaries will include data from all treatment groups. Data from the same treatment group will be combined across cohorts, and cohort will be added as a term in the statistical models.
4. Main Cohort (Cohort A) and Cohort D combined: These analyses will provide sensitivity analyses for the 300 mg ponesegromab treatment group, in participants with any serum GDF-15 concentration. Both summaries and statistical models will include data from the 300 mg ponesegromab treatment group and placebo only. Data from the same treatment group will be combined across cohorts, and cohort will be added as a term in the statistical models.

The analyses related to the primary, secondary and exploratory endpoints will be based on the appropriate population for analysis (see Section 4).

Unless otherwise stated, all summaries and plots will be presented by treatment group. The following treatment group labels (or similar) will be used:

DMB02-GSOP-RF02 7.0 Statistical Analysis Plan Template 31-Jan-2022

PFIZER CONFIDENTIAL

TMF Doc ID: 98.03

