**6.2.1. Change from baseline in KCCQ-23 CSS, OSS, TSS, and physical limitation at Week 22 (Cohorts A and C)**

Summaries and analyses will use efficacy approach 3 for all endpoints, as described in Section 5.2 and efficacy approach 1 for all endpoints other than CSS (which has already been detailed in Section 6.1).

KCCQ-23 CSS, OSS, TSS and physical limitation will each be summarized and analyzed across all timepoints, in a similar manner to the main analysis of the primary endpoint, as outlined in Section 6.1.1.1. This analysis will estimate the treatment effect related to Estimand 2 (as described in Section 2.2.4). Note that for efficacy approach 3, cohort will be included as a term in the statistical model.

For KCCQ-23 CSS score, a supplementary analysis will also be performed. The summaries and analysis will mirror that described above, but will be restricted to participants with a KCCQ-23 CSS score at baseline < 75.

**6.2.2. Response as defined by a  $\geq 5$ -point increase from baseline in KCCQ-23 CSS, OSS, TSS, and physical limitation at Week 22 (Cohorts A and C)**

Summaries and analyses will use efficacy approaches 1 and 3 for all endpoints, as described in Section 5.2.

Responses as defined by a  $\geq 5$ -point increase in KCCQ-23 CSS, OSS, TSS, and physical limitation score will be summarized descriptively by treatment group and timepoint, as described in Section 5.2.2, with no imputation for missing data. Tables will include all post-baseline timepoints. Plots of the percentages over time will also be produced, with all treatments on the same plot for each score.

The percentage of responses (and 90% CIs) at Week 22 will also be reported by treatment after multiple imputation for missing values as per Section 5.3.4. These responses *will also be analyzed separately using Estimand 3 and a logistic regression model* with multiple imputation (as described in Section 5.2.4), where missing values will be imputed using multiple imputation as per Section 5.3.4. *The logistic regression model will be fitted to the data at Week 22 only.* Note that for efficacy approach 3, cohort will be included as a term in the statistical model.

For KCCQ-23 CSS score, a supplementary analysis will also be performed. The summaries and analysis will mirror that described above, but will be restricted to participants with a KCCQ-23 CSS score at baseline < 75.

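### The 100 mg comparison matches the precision of the 300 mg comparison only if cohort is ignored; the SAP's cohort term reduces it to about 104–133 per arm, against 161

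*Protocol*

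**What the plan says.** Protocol Section 9.5 bases the size of Cohort C on the primary efficacy endpoint. It says that the 165 Cohort C completers, combined with the 100 mg and placebo completers of Cohort A, give a result that "gives similar acceptable Operating Characteristics to those for the 300 mg Q4W arm in the Main Cohort". Section 4.2 makes a weaker statement: the sample sizes "were chosen to provide acceptable operating characteristics for the primary endpoint for both doses", in support of dose-finding.

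The main analysis for 100 mg is approach 3 in SAP Section 5.2. It pools Cohorts A and C, includes all three doses and placebo, and specifies that "cohort will be added as a term in the statistical models". SAP Section 6.2.1, which covers KCCQ-23 CSS, repeats the requirement: "Note that for efficacy approach 3, cohort will be included as a term in the statistical model". The example MMRM code in SAP Appendix 4 enters cohort as a main effect, without a cohort-by-time interaction. Protocol Section 9.3.1.1 is looser and lists cohort among terms that are optional. SAP Section 2.1 reports no modifications to the protocol's analysis plan.

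**The concern.** The two cohorts have very different allocation. Most 100 mg participants are in Cohort C, and most placebo participants are in Cohort A. Simple pooling lets the large Cohort A placebo group act as a full control for Cohort C's 100 mg participants. A cohort term removes much of that benefit, because few Cohort A participants receive 100 mg. A precision statement that fits simple pooling may therefore not fit the analysis that will be run.

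At stake is the stated justification for randomizing about 195 further people, and the reading of the two doses side by side. If 300 mg reaches significance and 100 mg does not, a reader who was told that their operating characteristics are similar may see a dose effect where part of the difference is precision.

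**Working it through.** **Inputs from the documents**

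- Cohort A completers: "approximately 161 evaluable participants in the 300 mg Q4W and placebo Q4W treatment arms", which is 190 × 0.85 = 161.5 in each arm; and "approximately 15 evaluable participants in the 100 mg and 200 mg Q4W treatment arms", which is 18 × 0.85 = 15.3 in each arm.
- Cohort C: "130 participants randomly assigned to ponsegromab 100 mg Q4W and 65 to placebo Q4W in approximately a 2:1 ratio", leading to "approximately 110 evaluable participants in the 100 mg Q4W and 55 in the placebo Q4W treatment arms" (130 × 0.85 = 110.5; 65 × 0.85 = 55.25).
- Test level: one-sided 5% (SAP Section 5.1).
- Post-baseline KCCQ-23 visits: Weeks 4, 8, 12, 16, 20 and 22 (Protocol Table 5).

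**Assumptions.** The within-person correlation is not given; I use 0.4 to 0.9. The SD is set to 1, completers have all six visits, and the other covariates are left out.

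**Measure.** Equivalent number per arm m = 2 / Var(difference at Week 22).

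**Step 1: simple pooling.** 300 mg against placebo in Cohort A is 161 against 161, so m = 161. For 100 mg, 15 + 110 = 125 against 161 + 55 = 216. The variance is 1/125 + 1/216 = 0.01263, so m = 158.4. This is within 2% of 161 and reproduces the protocol's statement.

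**Step 2: cohort adjusted at Week 22 only, or by time.** The share in Cohort C is 110/125 = 0.880 on 100 mg and 55/216 = 0.255 on placebo, a difference of 0.625. The information on the cohort effect at one visit is 15 × 110/125 + 161 × 55/216 = 13.2 + 41.0 = 54.2. Adjustment adds 0.625²/54.2 = 0.00722 to the variance, giving 0.01985 and m = 100.8. The stratified sum agrees: 2 × (15 × 161/176 + 110 × 55/165) = 2 × (13.72 + 36.67) = 100.8.

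**Step 3: cohort as a main effect in the six-visit MMRM.** All six visits now inform one cohort effect, so the added 0.00722 is multiplied by f, the variance of the best weighted mean over the visits. Under compound symmetry, f = (1 + 5ρ)/6. Under AR-type correlation with ρ per 4 weeks, f = 1/[1 + Σ(1 − r)/(1 + r)] over the five gaps, with r = ρ for the four 4-week gaps and r = √ρ for the 2-week gap.

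| Correlation | f | Variance | m per arm |
|---|---|---|---|
| AR-type, 0.4 | 0.340 | 0.01508 | 132.6 |
| AR-type, 0.8 | 0.667 | 0.01744 | 114.7 |
| AR-type, 0.9 | 0.809 | 0.01846 | 108.3 |
| Compound symmetry, 0.4 | 0.500 | 0.01624 | 123.2 |
| Compound symmetry, 0.5 | 0.583 | 0.01684 | 118.8 |
| Compound symmetry, 0.8 | 0.833 | 0.01864 | 107.3 |
| Compound symmetry, 0.9 | 0.917 | 0.01924 | 103.9 |
| Zero (extreme case) | 0.167 | 0.01383 | 144.6 |

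Generalized least squares with all four arms gives the same figures.

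**Step 4: standard error and power.** The SE ratio to 300 mg is √(161/m). With equal true effects, power is Φ[(1.645 + z) × √(m/161) − 1.645], where z is 1.282 if 300 mg has 90% power and 0.842 if it has 80%. For m = 103.9 and 90%: 2.927 × 0.803 − 1.645 = 0.706, so power is 76%.

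| m | SE ratio | 100 mg power if 300 mg has 90% | if 300 mg has 80% |
|---|---|---|---|
| 132.6 | 1.10 | 84% | 73% |
| 103.9 | 1.24 | 76% | 64% |
| 100.8 | 1.26 | 75% | 63% |

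**The case against.** The strongest objection is redaction. The effect size, the SD and the operating characteristics are hidden, and they need not be power at one-sided 5%. A reader might infer from the closeness of 158 to 161 that the sponsor pooled without cohort and made an arithmetic slip. The documents do not show that: no stated count is miscalculated, and the sponsor may have allowed for cohort or meant *similar* loosely. This stands as a limit on what can be said about intent. It does not rescue the word, because no correlation in the table brings the cohort-adjusted figure near 161.

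A reader might also take about 101 per arm as the figure for KCCQ-23 CSS change, on the view that a cohort term leaves within-cohort information only. That is too strong. The Appendix 4 model has no cohort-by-time term, so earlier visits inform the cohort effect and the Cohort A placebo group contributes. The 101 is exact for adjustment at Week 22 alone or by time. It is an approximate guide for the responder model, which is fitted at Week 22 only.

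Nor do the documents support saying that the design fails Section 4.2. That section claims acceptability, not similarity, and its threshold is not visible.

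The protocol makes the cohort term optional, and its Section 9 allows the SAP to modify the analysis. So the SAP governs, but the precision statement was not updated to match. Dropping the term would restore the 158 only by setting mostly Cohort C 100 mg participants against mostly Cohort A placebo participants, which gives up the protection of randomization within cohort.

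Finally, 100 mg is a secondary comparison, and its 90% interval will show its precision. Both are true and bear on severity.

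**Conclusion.** The concern holds, at moderate severity. Under the analysis the SAP requires, the 100 mg contrast for KCCQ-23 CSS at Week 22 is worth about 104–133 per arm, a loss of about 18–35% against 161 (1 − 132.6/161; 1 − 103.9/161). The SE is about 10–24% larger than for 300 mg, or 26% at 101 per arm. The range rests on the planned completers and on an assumed within-person correlation of 0.4–0.9, under compound symmetry or AR-type decay. The direction does not depend on that assumption: even zero correlation gives only 144.6. The power figures use 80% and 90% for 300 mg as reference points, because the actual design values are redacted.

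The primary 300 mg inference uses Cohort A alone and is untouched. What fails is the visible description of the 100 mg comparison, whatever lies behind the redaction.

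**What to change.** Keep the cohort term and the planned enrolment. Recompute the 100 mg operating characteristics under the SAP's cohort-adjusted model, state the within-person correlation assumed, and put that result in Protocol Section 9.5 in place of *similar*. If the redacted figures already allow for cohort, say so and give them. Reconcile Protocol Section 9.3.1.1, where cohort is optional, with SAP Sections 5.2 and 6.2.1, where it is mandatory, and record the difference in SAP Section 2.1 if it remains. Section 4.2 needs a change only if the recomputed figures are no longer acceptable to the sponsor.

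The cost is one recalculation and text edits. The stated 100 mg figures will look less favourable if the present ones ignore cohort.

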10. SUPPORTING DOCUMENTATION AND OPERATIONAL CONSIDERATIONS

10.1. Appendix 1: Regulatory, Ethical, and Study Oversight Considerations

10.1.1. Regulatory and Ethical Considerations

This study will be conducted in accordance with the protocol and with the following:

- Consensus ethical principles derived from international guidelines, including the Declaration of Helsinki and CIOMS International Ethical Guidelines;
- Applicable ICH GCP guidelines;
- Applicable laws and regulations, including applicable privacy laws.

The protocol, protocol amendments, ICD, SRSD(s), and other relevant documents (eg, advertisements) must be reviewed and approved by the sponsor, submitted to an IRB/EC by the investigator, and reviewed and approved by the IRB/EC before the study is initiated.

Any amendments to the protocol will require IRB/EC approval before implementation of changes made to the study design, except for changes necessary to eliminate an immediate hazard to study participants.

Protocols and any substantial amendments to the protocol will require health authority approval prior to initiation except for changes necessary to eliminate an immediate hazard to study participants.

The investigator will be responsible for the following:

- Providing written summaries of the status of the study to the IRB/EC annually or more frequently in accordance with the requirements, policies, and procedures established by the IRB/EC;
- Notifying the IRB/EC of SAEs or other significant safety findings as required by IRB/EC procedures;
- Providing oversight of the conduct of the study at the site and adherence to requirements of 21 CFR, ICH GCP guidelines, the IRB/EC, European regulation 536/2014 for clinical studies, European Medical Device Regulation 2017/745 for clinical device research, and all other applicable local regulations.

10.1.1.1. Reporting of Safety Issues and Serious Breaches of the Protocol or ICH GCP

In the event of any prohibition or restriction imposed (ie, clinical hold) by an applicable regulatory authority in any area of the world, or if the investigator is aware of any new information that might influence the evaluation of the benefits and risks of the study intervention, Pfizer should be informed immediately.

In addition, the investigator will inform Pfizer immediately of any urgent safety measures taken by the investigator to protect the study participants against any immediate hazard, and of any serious breaches of this protocol or of the ICH GCP guidelines that the investigator becomes aware of.

10.1.2. Financial Disclosure

Investigators and sub-investigators will provide the sponsor with sufficient, accurate financial information as requested to allow the sponsor to submit complete and accurate financial certification or disclosure statements to the appropriate regulatory authorities. Investigators are responsible for providing information on financial interests during the course of the study and for 1 year after completion of the study.

10.1.3. Informed Consent Process

The investigator or their representative will explain the nature of the study, including the risks and benefits, to the participant and answer all questions regarding the study. The participant should be given sufficient time and opportunity to ask questions and to decide whether or not to participate in the trial.

Participants must be informed that their participation is voluntary. Participants will be required to sign a statement of informed consent that meets the requirements of 21 CFR 50, local regulations, ICH guidelines, privacy and data protection requirements, where applicable, and the IRB/EC or study center.

The investigator must ensure that each study participant is fully informed about the nature and objectives of the study, the sharing of data related to the study, and possible risks associated with participation, including the risks associated with the processing of the participant's personal data.

The participant must be informed that their personal study-related data will be used by the sponsor in accordance with local data protection law. The level of disclosure must also be explained to the participant.

The participant must be informed that their medical records may be examined by Clinical Quality Assurance auditors or other authorized personnel appointed by the sponsor, by appropriate IRB/EC members, and by inspectors from regulatory authorities.

The investigator further must ensure that each study participant is fully informed about their right to access and correct their personal data and to withdraw consent for the processing of his or her personal data.

The medical record must include a statement that written informed consent was obtained before the participant was enrolled in the study and the date on which the written consent was obtained. The authorized person obtaining the informed consent must also sign the ICD.

Participants must be reconsented to the most current version of the ICD(s) during their participation in the study.

A copy of the ICD(s) must be provided to the participant.

Participants who are rescreened are required to sign a new ICD.

10.1.4. Data Protection

All parties will comply with all applicable laws, including laws regarding the implementation of organizational and technical measures to ensure protection of participant data.

Participants' personal data will be stored at the study site in encrypted electronic and/or paper form and will be password-protected or secured in a locked room to ensure that only authorized study staff have access. The study site will implement appropriate technical and organizational measures to ensure that the personal data can be recovered in the event of disaster. In the event of a potential personal data breach, the study site will be responsible for determining whether a personal data breach has in fact occurred and, if so, providing breach notifications as required by law.

To protect the rights and freedoms of participants with regard to the processing of personal data, participants will be assigned a single, participant-specific numerical code. Any participant records or data sets that are transferred to the sponsor will contain the numerical code; participant names will not be transferred. All other identifiable data transferred to the sponsor will be identified by this single, participant-specific code. The study site will maintain a confidential list of participants who participated in the study, linking each participant's numerical code to his or her actual identity and medical record ID. In case of data transfer, the sponsor will protect the confidentiality of participants' personal data consistent with the clinical study agreement and applicable privacy laws.

Information technology systems used to collect, process, and store study-related data are secured by technical and organizational security measures designed to protect such data against accidental or unlawful loss, alteration, or unauthorized disclosure or access.

The sponsor maintains SOPs on how to respond in the event of unauthorized access, use, or disclosure of sponsor information or systems.

